14.0 BIOSTATISTICS

Target sample size is 24 patients, wherein 12 patients will be randomized to topical ruxolitinib to right side and 12 patients to the left side, with placebo cream on contralateral side. For each side of the face/body, non-sclerotic and superficially sclerotic chronic cutaneous GVHD BSA, PGA, and CAILS will be assessed in real-time by the study dermatologist observer blinded to the treatment status. The methodology for the real-time BSA calculation is available in Appendix I,II. The efficacy endpoint for the primary objective will be the difference in body surface area (BSA) as recorded by the dermatologist of non-sclerotic and superficially sclerotic cutaneous cGVHD between the topical ruxolitinib and vehicle treated sides of the face/body at study day 28. In this pilot study, we are utilizing three different measures to assess efficacy to qualitatively evaluate which works best for the clinician within the context of the patient visit. The bone marrow transplantation oncologist will subsequently calculate the BSA via total body photographs taken during the visit. Maximum BSA for topical ruxolitinib application will be 20% of overall BSA. All BSA, PGA, and CAILS assessments performed at study days 14 ± 3 days and study day 28 ± 3 days will be performed by the study dermatologist in real-time and serve as the data for the efficacy analysis. All BSA will also be calculated virtually by one bone marrow transplantation hematologist in review of total body photographs performed during visit, blinded to treatment, but will not contribute to efficacy assessments. Participants will only be included in the primary endpoint analysis if they complete the 28 ± 3 days assessment. Descriptive statistics and graphical methods will be employed to evaluate participant characteristics and the distribution BSA, PGA, and CAILS differences at each evaluation time point. Paired t-tests will be performed to assess differences in BSA. In addition, since the overall area treated may vary slightly between participants, we will use linear regression with the difference between treatment and control areas at day 28 as the dependent variable, and the total

**MEMORIAL SLOAN KETTERING CANCER CENTER
IRB PROTOCOL**

treatment area BSA as the independent variable. Regression coefficients along with 95% confidence intervals will be reported for this treatment area adjusted difference.

The primary aim is to assess the efficacy of ruxolitinib 1.5% cream for the treatment of non-sclerotic and superficially sclerotic chronic cutaneous GVHD at day 28 visit. This is a pilot study. With the average body surface area for male and female adult cancer patients has been estimated to be 1.9m² and 1.7m², respectively[26]. Using an average BSA of 1.8m² (18,000 cm²) for our mixed sample; if we treat, on average, 5.0% BSA per participant, we expect to have equivalent areas of 0.09m² or 900cm² of treatment and control areas per participant.

Table. Effect size calculations for the minimum detectable difference in area between treatment and control sides of the participant based on varying levels of correlation between treatment and control areas within participant.

Effect Size	Difference in area between treatment and control areas (cm ²)	Control area (cm ²)	Treatment area (cm ²)	SD of the difference	SD Control area	Correlation between treatment and control areas
-0.5972	-400.6	900	499.4	670.8	500	0.1
-0.5972	-377.7	900	522.3	632.5	500	0.2
-0.5972	-353.3	900	546.7	591.6	500	0.3
-0.5972	-327.1	900	572.9	547.7	500	0.4
-0.5972	-298.6	900	601.4	500	500	0.5
-0.5972	-267.1	900	632.9	447.2	500	0.6
-0.5972	-231.3	900	668.7	387.3	500	0.7
-0.5972	-188.8	900	711.2	316.2	500	0.8

So, based on these estimates, if we select lesional areas on a patient equivalent to 5% BSA (which is roughly 900cm² for both treatment and control sides), and we have an estimated common standard deviation of 500, with 80% power, a two-sided test, an alpha level of 5%, and a correlation between treatment and control areas of 0.4, we can expect to detect a 327.1cm² difference between treatment and control areas at the day 28 evaluation. The effect size calculation is based on a paired t-test. Since we do not have any pilot data for these calculations, the estimate for the standard deviation that utilized for these estimates comes from experience with conditions with a similar presentation. The Table above lists the expected differences between treatment and control areas based on a range of correlations.

Secondary endpoints include:

1. Physician's Global Assessment of Clinical Condition (PGA) at day 28

The difference in the PGA score of non-sclerotic and superficially sclerotic cutaneous cGVHD between the topical ruxolitinib and vehicle treated sides of the face/body will be calculated. The Wilcoxon signed rank test will be used to assess differences in these paired assessments for the day 28 assessment.

MEMORIAL SLOAN KETTERING CANCER CENTER IRB PROTOCOL

2. Composite Assessment of Index Lesion Severity (CAILS)

The difference between the ratios of the day 28 CAILS score to baseline CAILS score of non-sclerotic and superficially sclerotic cutaneous cGVHD between ruxolitinib treated side and vehicle treated sides of the face/body at study completion. We will use descriptive statistics to describe the distribution of the difference in CAILS ratios between treated and vehicle sides of the body. The difference in ratios will be assessed using a paired t-test.

3. Efficacy at day 14

Little is known about the efficacy of this treatment in this patient population. As a secondary aim, we will assess efficacy at the 14 day visit as we described for the primary aim of the study using paired t-tests and linear regression to control for potential differences in overall treatment areas between study participants.

4. Patient-reported Outcomes

Patient reported outcomes measured by the NCI Patient Reported Outcomes-Common Terminology Criteria for Adverse Events (PRO-CTCAE™) for each side of face/body affected by GVHD rash; a Likert-scale patient-reported assessment of change in the treated areas has been appended to adapt the PRO-CTCAE™ for this study. PRO-CTCAE™ instrument will be scored as ascribed by methods published for this instrument. Overall summary measures and subdomain measures will be summarized using descriptive statistics. To evaluate differences in the paired responses, for the overall PRO-CTCAE score and for each of the subdomain scores, the Wilcoxon signed rank test will be used.

5. Agreement between GVHD BSA Measurements

GVHD BSA measurements will be evaluated during the patient visit by a dermatologist, and by an additional bone marrow transplant physician using digital clinical images captured during the patient visit. The GVHD BSA assessments for both evaluations will be visually assessed using scatterplots of the two independent assessments and compared using Lin's concordance correlation coefficient.

6. Safety and Tolerability

All patients will be evaluable for adverse events (toxicities) from the time of their first treatment with ruxolitinib until the end of the study visits or until they are lost to follow-up. All reported adverse events (AEs grade ≥ 2 with any attribution) during the study period through day 56 follow-up [and day 84 \pm 5 days for subjects who continue in the open-label extension] visit will be coded using Medical dictionary for regulatory activities (MedDRA) Version 20.0. For all adverse events, all treatment-emergent adverse events, all serious adverse events, and all adverse leading to discontinuation frequency distributions by system organ class and preferred term will be calculated and presented for each patient and each treatment side, when applicable. The safety of all patients enrolled in this study will be monitored throughout the study, and at safety visit 28 \pm 5 days following the last study dose. Safety monitoring will include history and physical examination with adverse event reporting. A follow-up safety evaluation will be done until end of study visit after discontinuing topical ruxolitinib cream treatment or withdrawal from the study for any reason. In addition, patients should notify the study staff of any problems that occur between visits by telephone and, if

**MEMORIAL SLOAN KETTERING CANCER CENTER
IRB PROTOCOL**

necessary, be evaluated by the Investigator or study staff at an unscheduled interim hospital visit.

Treatment adjustments: Patients who report or exhibit treatment-related AEs should have their treatment exposure reduced or discontinued. If no frequency of study drug application is tolerated for any of the patient's lesional skin, then the patient must be withdrawn from the study. Treatment interruptions for non-medical reasons are at times unavoidable and are permissible under this protocol but must be documented. However, every attempt should be made to avoid any non-medical treatment delays

- Grade 1 – 2: No change to study drug dose. Continue clinical monitoring.
- Grade 3 (with attribution possibly, probably, or definitely related): Hold study drug until AE improves to grade ≤2.
- Grade 4 (with attribution possibly, probably, or definitely related): Discontinue study drug.

Adverse Event Definitions

The following definitions of terms guided by the International Conference on Harmonization and the US Code of Federal Regulations apply to this section:

An adverse event (AE) is any untoward medical occurrence in a patient or clinical investigation subject administered a pharmaceutical product that does not necessarily have a causal relationship with this treatment.

Serious adverse event (SAE) is any adverse event that is fatal or life-threatening, is permanently disabling, requires or prolongs inpatient hospitalization, or is a congenital anomaly, or any important medical event.

- Life-threatening, for the purpose of reporting adverse events, refers to an event in which the patient was, in the view of the initial reporter, at immediate risk of death at the time of the event as it occurred (i.e., it does not refer to an event which might have resulted in death if it were more severe).
- Hospitalization describes a period of at least 24 hours. Over-night stay for observation, stay at emergency room or treatment on an out-patient basis do not constitute a hospitalization. However, medical judgment must always be exercised and when in doubt the case should be considered serious (i.e. if case fulfills the criterion for a medically important event).
 - Hospitalizations for administrative or social purposes do not constitute a serious adverse event.
 - Hospital admissions and/or surgical operations planned before trial inclusion are not considered AEs, if the illness or disease existed before the subject was enrolled in the trial, provided that the condition did not deteriorate during the trial. Associated with the use of the drug means that there is a reasonable possibility that the event may have been caused by the drug.

Toxicity information will be presented on an individual basis and will be summarized using descriptive statistics.

7. Accrual, retention and compliance with therapy

Since this study involves a novel patient population for our department, we will evaluate metrics on the number of patient accrued relative to the number approached. We will also assess retention at each study time point. Compliance with application of the study

MEMORIAL SLOAN KETTERING CANCER CENTER
IRB PROTOCOL

medications will be assessed via patient logs.

Descriptive statistics will be provided for patient characteristics, efficacy, patient-reported outcomes, safety and tolerability, and minimally invasive skin tape strip molecular profiles as appropriate. Patients will be evaluable for the efficacy assessment if they complete the 28 day (+/-3 day) assessment. If patients miss other planned assessments, they will still be evaluable for the primary objective.

We expect to accrue 1 – 4 patients per month, and expect to complete enrollment in 6-26 months.

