9.0 TREATMENT/INTERVENTION PLAN

Patients will be prescribed twice daily use of topical ruxolitinib 1.5% cream (randomized half of face/body) and vehicle/moisturizer (for contralateral side of face/body) to a maximum of 20% BSA on each side for 28 ± 3 days. Topical ruxolitinib will be provided as topical cream.

In the morning and evening (at least 60 minutes before bedtime), patients will be instructed to apply a pre-designated number of fingertip units of each topical intervention (ruxolitinib and moisturizer) to each side of the face/body unit as outlined in provided photograph for each side. Patients will receive detailed instructions at the baseline visit and receive clear, written instructions on the standardized application technique (see Patient Instructions: Topical Medications). Patients will apply topical ruxolitinib cream and vehicle cream to the equivalent BSA on each side (e.g., if one side has

MEMORIAL SLOAN KETTERING CANCER CENTER IRB PROTOCOL

15% lesional skin and contralateral side has 10% lesional skin, the subject will treat only 10% on each side) and no more than to 20% BSA on each side.

Before topical applications, patients will be instructed to gently wash the face and body with a gentle cleanser (examples include Cetaphil, Purpose, Aveeno, Vanicream products) and pat skin dry with a clean towel. Patients will not be encouraged to apply topical emollients to the treated face and body during the study, but if desired, they may apply to untreated areas. Patients will be advised not to use products with chemicals or perfumes.

We do not anticipate the need for any adjustments to the treatment plan as consequence of adverse reactions to ruxolitinib (see section 11.0), but any patients with adverse cutaneous reactions to treatment with topical ruxolitinib 1.5% cream, or moisturizer will be advised to return to clinic to see a dermatologist right away. Adverse event reporting will be based on CTCAE v5.0, as applicable[22].

In the event of a patient emergency, the principal investigator and study pharmacist will be able to unblind the patient.

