12.0 CRITERIA FOR THERAPEUTIC RESPONSE/OUTCOME ASSESSMENT

The primary outcome of this study is the difference in body surface area (BSA) (Appendix I-II) of non-sclerotic and superficially sclerotic cutaneous cGVHD between ruxolitinib treated side and vehicle treated sides of the face/body at study completion (day 28 ± 3 days). Clinical assessment at all study visits, including baseline BSA will be performed by a dermatologist ([name], [name], [name], or [name]), and subsequently BSA will be calculated via photos by a single bone marrow transplantation hematologist.

Criteria for evaluation of clinical efficacy

No validated instruments for clinical assessment of chronic cutaneous GVHD exist[24]; we propose to use efficacy criteria that have been previously developed for evaluation of cutaneous T-cell lymphoma[25]. The body surface area (BSA) is the primary endpoint of efficacy. Secondary endpoints of efficacy include: Physician's Global Assessment of Clinical Condition (PGA), or the Composite Assessment of Index Lesion Severity (CAILS) grading scales are the secondary end points of efficacy[25]. The PGA will be the investigators' subjective assessment of the overall improvement or worsening in disease compared with the baseline assessment[25].

The CAILS assessment will generate a separate composite score for the treated and non-treated sides of the study participant. The assessment data to generate the composite score will be generated from case report form from the study visit. The treatment and vehicle sides of the body will be assessed for erythema, scaling, pruritus and size. For erythema, scaling and pruritus, the following grading system will be used.

CAILS Grading Tool for Erythema, Scaling, Pruritus [25]

MEMORIAL SLOAN KETTERING CANCER CENTER
IRB PROTOCOL

Scale	Grade
0	No evidence of sign or symptom
1	Intermediate interval
2	Mild: less than average presentation of sign or symptom
3	Intermediate interval
4	Moderate: average disease presentation of sign or symptom
5	Intermediate interval
6	Severe: >25% worse than average severity of sign or symptom
7	Intermediate interval
8	Very severe: the near worst severity of sign or symptom

*Intermediate intervals 1, 3, 5, and 7 serve as midpoints between the defined grades of 0, 2, 4, 6 and 8.

An estimate for the % involvement of the right and left areas will be assessed on scale of 0 to 11 as follows:

CAILS Grading Tool for BSA Involvement

Grade	BSA within marked treatment area on each side
0	0

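### The primary endpoint wording does not say whether day-28 BSA is read over the whole side or only inside the matched marked area, and the primary test has no baseline term to protect the comparison if it is the whole side

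*Combined protocol and SAP*

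**What the plan says.** Section 14.0 sets the efficacy endpoint as "the difference in body surface area (BSA) as recorded by the dermatologist" between the two treated sides of the face/body at day 28. The test is equally brief: "Paired t-tests will be performed to assess differences in BSA". The only planned adjustment is a linear regression of the day-28 difference with total "treatment area BSA as the independent variable". Day-1 BSA by side is collected (sections 8.0 and 10.0) but enters neither analysis.

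Section 2.0 and both statements of the primary outcome in section 12.0 also speak of the side of the face/body, with no limit to a marked area.

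Section 9.0 allows the sides to differ in total rash. In its example one side has "15% lesional skin and contralateral side has 10% lesional skin, the subject will treat only 10% on each side".

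Other places point to matched areas:
- Section 4.2 has same-size left and right lesional areas demarcated and evaluated, and uses one BSA value for both sides.
- Section 10.2 ties the dermatologist's BSA to what is targeted with topical therapy, calls the photographic reading treatment-targeted, and keeps the marked areas fixed.
- Section 14.0 sizes the trial on equal areas of 900 cm² per side.
- The CAILS size item in section 12.0 is the only one that states the limit outright: "BSA within marked treatment area on each side".

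**The concern.** Two dermatologists could follow the text faithfully and record different numbers for the same patient. One would read rash inside the outline and the other all rash on that side, and section 12.0 allows more than one dermatologist to assess.

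The difference matters because the primary test uses day-28 values only. With whole-side BSA, rash that nobody treated enters the side difference as noise. The regression does not help. Total treatment area is the same on both sides by design and carries no sign, so it cannot show which side had the surplus. CAILS, by contrast, is analysed as a ratio to baseline, so the primary endpoint is the less protected of the two. What is at stake is the precision of a 24-patient estimate.

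**Working it through.** **Inputs from section 14.0.** "Target sample size is 24 patients"; "with 80% power, a two-sided test, an alpha level of 5"%; "we have an estimated common standard deviation of 500" cm² per side; correlation 0.4; total skin surface 18,000 cm², so 1% BSA = 180 cm².

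**Step 1: the plan's own figure.** SD of the difference = 500 × √(2 × (1 − 0.4)) = 547.7 cm². Noncentral-t power for a paired t-test with n = 24 (23 df) and effect size 0.5972 is 0.800. Detectable difference = 0.5972 × 547.7 = 327.1 cm². The stated figure reproduces.

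**Step 2: marked areas, equal at baseline.** Let b be the common day-1 area, and T and C the day-28 areas on the ruxolitinib and vehicle sides. Then (T − b) − (C − b) = T − C. The raw day-28 difference equals the difference in change from baseline, the t statistic is the same, and power stays at 80%.

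**Step 3: whole-side BSA.** Assumptions, none given by the documents: the side difference in untreated rash has mean zero (side is randomised) and SD s, persists unchanged to day 28, and is not already inside the 547.7 cm². Then SD = √(547.7² + s²), the effect size is 327.1 / SD, and n = 24.

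| s (cm²) | s (% BSA) | SD of difference | Effect size | Power | n for 80% |
|---|---|---|---|---|---|
| 0 | 0 | 547.7 | 0.597 | 80% | 24 |
| 180 | 1 | 576.5 | 0.567 | 76% | 27 |
| 360 | 2 | 655.4 | 0.499 | 65% | 34 |
| 540 | 3 | 769.1 | 0.425 | 51% | 46 |

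**Step 4: what a baseline term recovers.** Simulate D = X + E for 24 patients, with X the day-1 side difference (mean 0, SD s) and E normal with mean −327.1 and SD 547.7. Regress D on X uncentred. The intercept is the effect at zero baseline difference: a = D̄ − bX̄ (b now the slope), with variance σ²(1/24 + X̄²/Sxx) and 22 df. Power is about 78% for s from 90 to 540 cm², and type I error is about 5%.

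**Step 5: centring.** If X is centred at its sample mean, the intercept becomes D̄, the raw mean difference, while its variance is taken as σ²/24. The chance imbalance X̄ stays in the estimate but is left out of its standard error. For s of 360 to 540 cm², type I error is about 9 to 15% at correlation 0.4 and 19 to 31% at 0.8. The covariate must therefore not be mean-centred.

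**The case against.** The strongest reply is that the design already deals with this. Section 4.2 says that same-size areas are evaluated, not merely treated. Section 10.2 places the fixed-area rule under the BSA bullet, where it would have little purpose if whole sides were read. The regression and the sample-size text in section 14.0 both speak of treatment and control areas. On this reading the surplus in the section 9.0 example lies outside the evaluated region, and a baseline covariate would be zero or close to it.

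Most of this stands as evidence of intent. It does not close the gap, because the endpoint sentences in sections 2.0, 12.0 and 14.0 omit the limit that the CAILS item states, and the wording in section 10.2 can attach to the side as easily as to an area.

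The objection to the arithmetic also stands. The documents give no SD for baseline imbalance. The plan's SD of 500 and its correlation may already include some, in which case Step 3 counts it twice.

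A reader might infer that the section 9.0 example puts 5% × 18,000 = 900 cm² of untreated rash into one patient's primary difference, or that the trial does not have its stated 80% power. The documents support neither as a finding. Both hold only if whole-side BSA is recorded, and the second also needs the assumed SDs.

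**Conclusion.** The point holds as an ambiguity in the primary endpoint with a conditional cost. The texts indicate two measurement regions and should be reconciled. If matched marked areas are read, nothing is lost. If whole sides are read, the primary difference gains variance that the planned regression cannot remove, and power at correlation 0.4 would be about 76%, 65% or 51% under the assumptions of Step 3. Randomising the side means that no systematic bias follows on either reading. Small day-1 differences inside the marked areas remain possible, and the documents give no figure for their size. The plan is a pilot for preliminary estimates, so this is a matter of clarity and precision, not a flaw that invalidates the design.

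**What to change.** In sections 12.0 and 14.0, with section 2.0 brought into line:

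1. Define primary BSA as lesional BSA within the fixed marked target area on each side, as the CAILS size item already does. This removes the ambiguity by itself.
2. Estimate the treatment effect as the intercept of a regression of the day-28 side difference (ruxolitinib minus vehicle) on the day-1 side difference, and state that the covariate is not mean-centred. Keep the raw paired t-test as supportive. If all day-1 differences are zero, the covariate drops out and the analysis is the paired t-test; say so in advance.

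Cost: wording only, since day-1 and day-28 BSA by side are already collected. The regression spends one degree of freedom, about 1 to 2 points of power if the sides are nearly matched.

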4.2 Intervention

Lesional areas will be chosen by the attending dermatologist. Lesional areas of the same corresponding size on the left and right hand sides of the participant will be evaluated, demarcated, imaged. In this study, participants will provide both treatment and vehicle control lesions. Eligible patients will be randomized to one of two treatment groups: Group 1 will be randomized to topical ruxolitinib BID to **left** side of face/body and topical moisturizer BID to **right** side of face/body; Group 2 will be randomized to topical ruxolitinib BID to **right** side of face/body and topical moisturizer BID to **left** side of face/body. Randomizing the treatment side is to maintain blinding of the physician. For example: if patients are all assigned to apply topical ruxolitinib to their right side and are showing clinical improvement on each patient's right side consistently, the physician will be aware that the right side is the treated side, possibly adding bias to the study. Variability in application side will also help to account for inter-patient variability in application with right- versus- left hand. Participants and their study doctor will be blinded from knowing which side of the face/body will be treated with the study cream, and which side of the face/body will be treated with the vehicle. For study purposes, Study Day 1 is defined as the first day of topical application. Patients will self-administer topical ruxolitinib and vehicle topically to affected rash area on directed side of face/body and record topical application on study diaries that will be provided by the study doctor or a member of the research team. On Study Day 28, end of treatment day, all patients will be eligible for the open label portion of the study. The attending will determine the patient's response, and if the patient wishes to continue, then they will be given the opportunity to use the topical ruxolitinib for an additional 28 days. If the patient wishes to continue then pharmacy will dispense open label ruxolitinib for the patient to apply to both sides of the body, not to exceed 20% total BSA. The PI, the Clinical Research Coordinator, and the patient will remain blinded to the initial treatment arm, but will become unblinded during the open label portion."

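### Side of application is randomised, but the primary paired t-test leaves the randomised left/right group out; if one side consistently does better, the analysis loses some precision, and the estimate shifts if the completers are split unequally

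*Combined protocol and SAP*

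**What the plan says.** Section 14.0 sets the design: "Target sample size is 24 patients, wherein 12 patients will be randomized to topical ruxolitinib to right side and 12 patients to the left side". Section 15.2 adds that allocation is by random permuted blocks; no block size is given. Sections 4.2 and 15.2 give the main reason for randomising side as keeping the physician blinded, and then a second one: "Variability in application side will also help to account for inter-patient variability in application with right- versus- left hand".

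For the analysis, section 14.0 says "Paired t-tests will be performed to assess differences in BSA". A supporting linear regression of the day-28 difference has total treatment area as its only covariate. Day-14 efficacy follows the primary approach, and the difference in CAILS ratios is tested with a paired t-test. No analysis includes the randomised left/right group, and no estimate of a side effect is planned.

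On sizing, section 14.0 assumes "an estimated common standard deviation of 500" and concludes, "with 80% power, a two-sided test, an alpha level of 5%, and a correlation between treatment and control areas of 0.4", that "we can expect to detect a 327.1cm² difference between treatment and control areas at the day 28 evaluation". It adds that "The effect size calculation is based on a paired t-test".

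Only patients who complete the day-28 assessment enter the primary analysis. Under section 13.0, patients removed for adverse events are not replaced. Those who withdraw consent, die or join a conflicting systemic trial are replaced.

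**The concern.** The design resembles a two-period crossover with side in place of period. Each patient supplies a ruxolitinib-minus-vehicle difference, and the randomised group decides which side carries which cream. If the right side does consistently better or worse than the left whichever cream is on it, that effect is added to the difference in one group and subtracted in the other.

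Allocating 12 patients each way makes this cancel in the mean. A pooled paired t-test still treats the gap between the two groups as random error, so the standard error is larger than the design requires. If the completers are not split evenly, the cancellation is also incomplete and the estimate moves.

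The objective is to obtain preliminary efficacy estimates, so the point estimate and its interval are the main product. The sizing sits at exactly 80% power, on an SD chosen without pilot data. What is at stake is precision, and a small shift under imbalance; false-positive control is not threatened.

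**Working it through.** **Inputs from section 14.0.** n = 24 (12/12); SD per side 500 cm²; correlation 0.4; two-sided alpha 5%; power 80%. **Assumed, because the documents give no figure:** delta = 100, 200 or 300 cm²; completer splits of 12/11 and 12/9; SD 547.7 cm² taken to exclude side variation.

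**Step 1, the plan's own figure.** SD of the difference = 500 × √(2 × (1 − 0.4)) = 547.7 cm². Exact paired-t power with 23 df reaches 80% at a standardised effect of 0.5972, and 0.5972 × 547.7 = 327.1 cm². The plan's figure reproduces.

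**Step 2, model.** D = τ + s·delta + e. Here D is ruxolitinib minus vehicle, τ is the treatment effect, s is +1 if ruxolitinib is on the right and −1 if on the left, and delta is the mean right-minus-left difference irrespective of cream. The SD of e is 547.7 cm².

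**Step 3, effect on the error term at 12/12.** Expected variance in the paired t-test = 547.7² + delta² × 24/23.
- delta 100: SD 557.1 (ratio 1.017)
- delta 200: SD 584.6 (ratio 1.067)
- delta 300: SD 627.6 (ratio 1.146)

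Multiplying each ratio by the ratio of t quantiles (23 df over 22 df: 2.0687/2.0739) gives intervals about 1.5%, 6.5% and 14.3% wider than with a group term. The average simulated widths agree: 1.5%, 6.6% and 14.5%.

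**Step 4, power and type I error at 12/12.** At 12/12 delta cancels from the mean, so its true sampling variance is unchanged and only the estimated SD is inflated. Putting the inflated SD into a noncentral t formula would therefore overstate the loss (74.7% at delta 200). Simulation with 200,000 runs per setting and a true difference of 327.1 cm² gives:

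| delta (cm²) | Power, paired t | Power, group term | Type I error, paired t |
|---|---|---|---|
| 100 | 79.0% | about 80% | 4.7% |
| 200 | 76.2% | about 80% | 3.7% |
| 300 | 70.8% | about 80% | 2.6% |

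With the group term, type I error is about 5% throughout.

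**Step 5, unequal completers.** Shift of the plain mean = delta × (nR − nL)/n.
- 12/12: zero.
- 12/11: delta × 1/23 = 4.3 cm² (delta 100) or 8.7 cm² (delta 200).
- 12/9: delta × 3/21 = 14.3 cm² or 28.6 cm².

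For comparison, the standard error at n = 21 is about 547.7/√21 = 119.5 cm². The mean of the two group means has no such shift. Type I error of the paired t-test at 12/9 with delta 200 is about 4.3%, still below 5%.

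**Step 6, cost of adjusting when delta is zero.** At 12/12 the model has 22 df: detectable difference 327.8 instead of 327.1 cm², power 79.8% instead of 80.0%. At 12/9 the interval is about 1.3% wider than the plain one.

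**The case against.** A paired t-test is a standard, valid analysis of within-patient differences, and here it matches the sizing. Nothing in the documents supports a large delta. Section 9.0 has equal areas treated on the two sides, with a pre-designated number of fingertip units. Against the plan's 900 cm² per side, a delta of 200 means an average shift of 22% of the treated area from side alone (200/900), and 300 means 33%. At 100 the power loss is about one point. The SD of 500 comes from experience with similar conditions. If it already contains side variation, the paired test keeps roughly its stated 80%, and a group term would instead raise power, to about 81% and 85% for delta 100 and 200. All of this stands, and it limits the size of the point.

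Four stronger readings are tempting, and the documents do not support them:
- **That the protocol predicts a systematic side effect.** It names only variability between patients in right- versus left-hand application, and relies on varying the side to help with it. It gives no direction or size.
- **That any hand effect causes this loss and a group term would cure it.** Effects that differ in sign between patients, for example with mixed hand dominance or caregiver application, are ordinary noise. A left/right term leaves them in.
- **That the planned estimate is biased.** The shift is zero at 12/12 and averages to zero if losses are unrelated to side group. Permuted blocks and the replacement of some removals limit imbalance; the 12/9 split is an assumption.
- **That the test is invalid.** Its type I error falls below 5% when a consistent side effect exists.

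What the objection does not answer is that the randomised factor appears in no model, although including it costs almost nothing.

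**Conclusion.** The point holds as one of efficiency, conditional on a consistent left/right effect. In that case the paired t-test gives up about 1, 4 and 9 points of power at delta 100, 200 and 300 cm², and its type I error falls below the nominal level. An uneven set of completers adds a shift that is small against the 327.1 cm² target: at most about 29 cm² at 12/9 with delta 200. These figures rest on the plan's correlation of 0.4, on an SD of 547.7 cm² that excludes side variation, and on assumed values of delta and of the split. If there is no consistent side effect, nothing is lost under the plan as written. The case for changing it is that the protection is nearly free and the result would be useful for planning a later trial.

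**What to change.** In section 14.0, analyse the within-patient day-28 BSA difference (ruxolitinib minus vehicle) with a linear model that includes the randomised group, coded +1/2 and −1/2. Report the intercept, with its 95% confidence interval and t-test on n − 2 df, as the treatment effect. This intercept is the mean of the two group means. Use the same term for the day-14 BSA and CAILS-ratio comparisons. Report the estimated side effect with its interval; with this coding the group coefficient estimates twice delta, so delta is half of it. Specify the model before unblinding so that it is not chosen on the results.

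The cost is a sentence or two in section 14.0 and one degree of freedom: a detectable difference of about 327.8 instead of 327.1 cm² at 12/12 with no side effect. If the split is unequal and there is no side effect, the interval is slightly wider, by about 1.3% at 12/9. No new data are needed.
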